9.1 Extent of Exposure

Frequency distribution of the duration (in days) of treatment with the IMP in the double-blind period (Phase B) (1-7, 8-14, 15-21, 22-28, 29-35, 36-42, and > 42) will be determined by treatment group and for the overall brexpiprazole group. Similar summarization will be performed for each requisite concomitant medication subgroup.

Frequency distribution of the duration (in days) of treatment with a requisite concomitant medication in the double-blind period (Phase B) (1-7, 8-14, 15-21, 22-28, 29-35, 36-42, and > 42) will be determined by treatment group and for the overall brexpiprazole group.

Descriptive statistics of the mean daily dose of each requisite concomitant medication in the double-blind period (Phase B) will be calculated by treatment group and for the overall brexpiprazole group.

Frequency distribution of the duration (in days) of treatment with a requisite concomitant medication in the antidepressant treatment period (Phase A) (1-7, 8-14, 15-21, 22-28, 29-35, 36-42, 43-49, 50-56, and > 56) will be determined overall and for each requisite concomitant medication in the ADT set.

Frequency distribution of the duration (in days) of treatment with a requisite concomitant medication in the antidepressant-responder treatment-continuation period (Phase A+) (1-7, 8-14, 15-21, 22-28, 29-35, 36-42, and > 42) will be determined overall and for each requisite concomitant medication in the Phase A+ set.

9.2 Adverse Events

All adverse events (AEs) will be coded by Medical Dictionary for Regulatory Activities (MedDRA) (Ver. 24.0) System Organ Class (SOC) and Preferred Term (PT). Numbers and proportions of subjects with the following AEs will be summarized by SOC and PT by treatment group and for the overall brexpiprazole group. If an AE occurs more than once in the same subject, the severest event will be used in summarization.

- Adverse events occurring after initiation of IMP administration in the double-blind period (Phase B) (treatment-emergent adverse events [TEAEs])
- TEAEs by severity
- TEAEs with an outcome of death
- Serious TEAEs
- TEAEs leading to discontinuation of the IMP
- TEAEs occurring in $\geq 2\%$ of subjects in any brexpiprazole group and more frequently than in the placebo group

- TEAEs by date of initial onset (1-7, 8-14, 15-21, 22-28, 29-35, 36-42, > 42, post-trial treatment)

TEAEs potentially causally related to the IMP will also be summarized in the same manner.

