5.2 Eliciting and Reporting Adverse Events

The investigator or subinvestigator will periodically assess subjects for the occurrence of AEs. To avoid bias in eliciting AEs, subjects should be asked the nonleading question: "How have you felt since your last visit?" For all AEs (serious and nonserious) reported by the subject, the event name, start and stop dates, severity, seriousness, relationship to IMP, actions taken regarding IMP administration, and outcome thereof must be recorded in the source documents and CRFs provided by the sponsor. Adverse event and SAE collection is to begin after a subject has signed the ICF. In this trial, AEs occurring during the screening period and the antidepressant treatment period (Phase A) will be assessed in comparison to the subject's condition at screening, and AEs occurring during the double-blind period (Phase B) and the antidepressant-responder treatment-continuation period (Phase A+) will be assessed in comparison to the subject's condition at Week 8 of the antidepressant treatment period (Phase A).

Use medical terminology in AE reporting. Adverse events should be reported as a single unifying diagnosis whenever possible or, in the absence of a unifying diagnosis, as individual signs or symptoms. Exacerbation or disease progression should be reported as an AE only if there are unusual or severe clinical features that were not present, or experienced earlier, or not expected based on the course of the condition. If a reported AE has worsened in severity or seriousness, it should be reported as a new AE on the CRF.

In addition, the sponsor must be notified immediately by e-mail, in principle, of any IREs according to the procedure outlined below, in Section 5.3 Immediately Reportable Events. Special attention should be paid to recording hospitalization and concomitant medications.

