CT-8.7.2	Incidence of Drug-related TEAEs During Phase B of at Least 2% in Any Brexpiprazole Group and Greater Than Placebo by MedDRA System Organ Class and Preferred Term (Safety Analysis Set)
CT-8.8.1	Incidence of TEAEs During Phase B by MedDRA System Organ Class, Preferred Term and Time to First Onset (Safety Analysis Set)
CT-8.8.2	Incidence of Drug-related TEAEs During Phase B by MedDRA System Organ Class, Preferred Term and Time to First Onset (Safety Analysis Set)
CT-8.9.1	Incidence of TEAEs for EPS (Safety Analysis Set)
CT-8.9.2	Incidence of TEAEs During Phase B for Neuroleptic Malignant Syndrome (Safety Analysis Set)
CT-8.9.3	Incidence of TEAEs During Phase B for Rhabdomyolysis and CPK Elevation (Safety Analysis Set)
CT-8.9.4	Incidence of TEAEs During Phase B for Seizures (Safety Analysis Set)

CT-8.9.5	Incidence of TEAEs During Phase B for Orthostatic Hypotension, Dizziness, and Syncope (Safety Analysis Set)
CT-8.9.6	Incidence of TEAEs During Phase B for Suicidality (Safety Analysis Set)
CT-8.9.7	Incidence of TEAEs During Phase B for Somnolence (Safety Analysis Set)
CT-8.9.8	Incidence of TEAEs During Phase B for Hypersensitivity (Safety Analysis Set)
CT-8.9.9	Incidence of TEAEs During Phase B for VTE (Thrombotic and Embolic Events) (Safety Analysis Set)
CT-8.9.10	Incidence of TEAEs During Phase B for Haematopoietic/Leukopenia (Safety Analysis Set)
CT-8.9.11	Incidence of TEAEs During Phase B for Effect on Glucose (Safety Analysis Set)
CT-8.9.12	Incidence of TEAEs During Phase B for Effect on Lipids (Safety Analysis Set)
CT-8.9.13	Incidence of TEAEs During Phase B for Effect on Weight (Safety Analysis Set)
CT-8.9.14	Incidence of TEAEs During Phase B for QT Prolongation (Safety Analysis Set)
CT-8.9.15	Incidence of TEAEs During Phase B for Manic Switch (Safety Analysis Set)
CT-8.9.16	Incidence of TEAEs During Phase B for Effect on Prolactin (Safety Analysis Set)
CT-8.10.1	Incidence of TEAEs During Phase B by MedDRA System Organ Class and Preferred Term, by ADT (Safety Analysis Set)
CT-8.10.2	Incidence of TEAEs During Phase B by MedDRA System Organ Class and Preferred Term, by Gender (Safety Analysis Set)
CT-8.10.3	Incidence of TEAEs During Phase B by MedDRA System Organ Class and Preferred Term, by Age (Safety Analysis Set)
CT-8.10.4	Incidence of TEAEs During Phase B by MedDRA System Organ Class and Preferred Term, by CYP2D6 Metabolism Status (Safety Analysis Set)

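### SAP 9.2's severest-event rule conflicts with the first-onset tables: followed literally, it dates an adverse event that worsens at its worsening, not at its onset

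*SAP*

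**What the plan says.** SAP 9.2 introduces its list of TEAE summaries with "Numbers and proportions of subjects with the following AEs will be summarized by SOC and PT by treatment group" and, before the list begins, gives the rule for repeats: "If an AE occurs more than once in the same subject, the severest event will be used in summarization". One entry in the list is "TEAEs by date of initial onset", split into 1-7, 8-14, 15-21, 22-28, 29-35, 36-42 and more than 42 days, plus a post-treatment category. Related TEAEs are to be handled the same way. SAP Appendix 5 titles the planned table CT-8.8.1 "Incidence of TEAEs During Phase B by MedDRA System Organ Class, Preferred Term and Time to First Onset"; CT-8.8.2 is its drug-related counterpart. No exception to the rule appears in SAP 9.2, in SAP section 14 on changes to the planned analyses, or in Appendix 5. Protocol 7.6.1 has no rule for repeated events.

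On data collection, Protocol 5.2 states: "If a reported AE has worsened in severity or seriousness, it should be reported as a new AE on the CRF". For all AEs it also requires that "the event name, start and stop dates, severity, seriousness, relationship to IMP, actions taken regarding IMP administration, and outcome thereof must be recorded".

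Protocol 3.2.2 gives the 2 mg arm 1 mg until the Week 1 assessments and 2 mg after them. Protocol 3.7.1.9 puts that visit at Day 8, plus or minus 1 day.

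**The concern.** Keeping the severest record is the right choice for a table by severity. It is the wrong choice for a table by first onset, because under Protocol 5.2 the severest record of an event that intensifies is a later record with a later start date. The only explicit selection rule in the SAP therefore points away from what the onset tables say they show.

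What is at stake is the reading of timing around the dose step. The boundary between the first two onset intervals lies next to the Week 1 visit. An event that began while a 2 mg subject was still taking 1 mg, and worsened after the step, could be read from the table as having begun after the step.

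**Working it through.** The plan states no figure on this point, so the check is of text and logic, followed by one illustration.

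**Step 1: what the rule selects.** Three constructed subjects, each with one preferred term:

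| Subject | Records | Interval, severest record | Interval, earliest record |
|---|---|---|---|
| A | mild Day 3, moderate Day 10 | 8-14 | 1-7 |
| B | moderate Day 10 only | 8-14 | 8-14 |
| C | moderate Day 3, mild Day 10 | 1-7 | 1-7 |

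Only subject A moves. A shift needs a later record that is more severe than the first, and the shift is always to a later date. If both records fall in the same interval, the cell does not change.

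**Step 2: which shifts bear on the dose step.** Only events that start in Days 1-7 and worsen in a later interval do so. An event that starts on Day 16 and worsens on Day 25 moves from 15-21 to 22-28, but its true onset was already after the step.

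**Step 3: illustration of size.** Inputs from the documents: 240 planned subjects in the 2 mg arm (Protocol 3.3.1); akathisia at 2 mg of 7.4% in trial 331-10-228 and 8.3% in trial 331-13-214 (Protocol 1.2.2.2 and 1.2.2.3). Assumed, with no source in the documents: 5% to 30% of akathisia cases start in Days 1-7 and worsen in a later interval.

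- Expected cases = 240 × incidence: 240 × 0.074 = 17.8 and 240 × 0.083 = 19.9, so about 18 to 20.
- Cases leaving Days 1-7 = cases × fraction: 17.8 × 0.05 = 0.9 at the low end and 19.9 × 0.30 = 6.0 at the high end, so about 1 to 6.

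**Step 4: what does not change.** Keeping one record per subject and preferred term, whichever it is, leaves the number of subjects with that term the same. Overall TEAE incidence is unaffected.

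**The case against.** The strongest reply is that the onset summary is labelled twice, as initial onset in SAP 9.2 and as first onset in Appendix 5. A specific label may reasonably override a general rule whose natural home is the severity table, and a programmer may use the earliest date without being told. This stands to the extent that misdating is not certain. It does not remove the conflict: the label names the quantity, the rule names the record, and the SAP does not say which prevails.

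A reader might infer that the rule would produce a false dose-step effect in the 2 mg arm. The documents do not support that. The rule acts in all three arms, and the 1 mg arm has the same starting dose with no step, so it is a concurrent comparator. The intervals do not isolate the step either: with the visit allowed on Days 7 to 9, an onset early in the 8-14 interval can precede the first 2 mg tablet. For akathisia the table is also not the only source on timing. DIEPSS, which has an akathisia item, is rated at every Phase B visit (Protocol 3.7.3.7) and reported by item and time point (SAP 9.7.2). Listing AE-1.1 covers the adverse events of randomized subjects.

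A reader might apply an assumed worsening rate to every akathisia case and take the result as the harm. That would count shifts within an interval and shifts wholly after the step, neither of which bears on the dose step.

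A reader might also infer that the rule drops milder records that were related, serious or led to stopping IMP. That requires selecting the severest record before filtering, and the SAP states no order. The ordinary reading of counting subjects with a given class of event is to filter first, and the separate listings CT-9.2.1 and CT-9.3.1 would help to show a dropped serious event or discontinuation.

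**Conclusion.** The point holds as a conflict between a stated rule and the tables it governs. If the rule in SAP 9.2 is followed as written, an AE that worsens is dated at its worsening in CT-8.8.1 and CT-8.8.2, always later than its true onset, in every arm. In the 2 mg arm, this can show an event that began on 1 mg in an interval after the Week 1 step.

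The number affected cannot be derived from the documents. The illustration of 1 to 6 akathisia cases out of about 18 to 20 rests on two things: that the overseas incidences carry over to this trial, and that the assumed 5% to 30% is right. The priority is minor. The tables are descriptive, no test or decision depends on them, and the underlying records can still be listed.

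**What to change.** In SAP 9.2:

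- Limit the severest-event rule to the by-severity tables.
- For CT-8.8.1, use the earliest treatment-emergent start date per subject and preferred term, whatever the severity.
- For CT-8.8.2, use the earliest related record.
- As a clarification only, state that the related, serious and IMP-discontinuation tables first select the qualifying records and then count each subject once.

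The cost is a sentence or two in the SAP and a change of sort order in the table programs. No new data are needed, and no efficacy analysis is touched.

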9.2.1 Adverse Events of Interest

Each adverse event of interest is defined in Appendix 4. Numbers and proportions of subjects with the following AEs of interest will be summarized by SOC and PT by treatment group and for the overall brexpiprazole group.

- Extrapyramidal AEs
- Neuroleptic malignant syndrome-related AEs
- Rhabdomyolysis
- Seizure-related AEs
- Orthostatic disorder-related AEs
- Suicide/suicide attempt-related AEs
- Oversedation-related AEs
- Hypersensitive symptom-related AEs
- Venous thrombosis
- Blood disorder-related AEs
- Glucose metabolism-related AEs
- Lipid metabolism-related AEs
- Body weight-related AEs
- QT interval prolongation-related AEs
- Manic switch-related AEs
- Prolactin increase-related AEs

9.2.2 Subgroup Analysis of Adverse Events

Numbers and proportions of subjects with TEAEs will be summarized by SOC and PT by treatment group and for the overall brexpiprazole group in each of the following subgroups:

- Requisite concomitant medication (duloxetine, escitalopram, fluvoxamine, milnacipran, paroxetine, sertraline, venlafaxine)
- Sex (male, female)
- Age (< 55, ≥ 55)
- CYP2D6 phenotype (IM, EM, PM, Unknown)

- Impact of COVID-19 pandemic (subjects from whom consent was obtained before 07 Apr 2020, those from whom consent was obtained on or after 07 Apr 2020)

9.2.3 Adverse Events in the Antidepressant Treatment Period (Phase A) and the Antidepressant-responder Treatment-continuation Period (Phase A+)

Numbers and proportions of subjects who experienced AEs in the antidepressant treatment period (Phase A) will be summarized by SOC and PT overall and for each requisite concomitant medication in the ADT set.

Numbers and proportions of subjects who experienced AEs in the antidepressant-responder treatment-continuation period (Phase A+) will be summarized by SOC and PT overall and for each requisite concomitant medication in the Phase A+ set.

9.3 Clinical Laboratory Data

For each quantitative laboratory parameter, descriptive statistics of actual measurements and changes from baseline at each time point and the last time point will be calculated for each treatment group and for the overall brexpiprazole group.

For each quantitative laboratory parameter, actual measurements will be classified as "lower than the lower limit of the reference range," "within the reference range," and "higher than the upper limit of the reference range" using the reference range specified by the central laboratory, and a shift table from baseline will be produced for each treatment group and for the overall brexpiprazole group.

For each qualitative laboratory parameter, a shift table from baseline will be produced for each treatment group and for the overall brexpiprazole group.

Numbers and proportions of subjects with laboratory test values not meeting the criteria for potentially clinically significant laboratory test values (Appendix 2) at baseline and meeting the criteria after treatment will be determined for each treatment group and for the overall brexpiprazole group. A listing of these subjects will be provided.

Numbers and proportions of subjects with postdose values of alanine aminotransferase (ALT), aspartate aminotransferase (AST), and total bilirubin (TBL) meeting Hy's Law criteria (ALT or $AST \geq 3 \times$ the upper limit of normal [ULN] and $TBL \geq 2 \times$ ULN) will be determined for each treatment group and for the overall brexpiprazole group. A listing of these subjects will be provided.

Numbers and proportions of subjects with a prolactin value not meeting the criteria of $> 1 \times$ ULN, $> 2 \times$ ULN, or $> 3 \times$ ULN at baseline and meeting the criteria after treatment

will be determined by sex for each treatment group and for the overall brexpiprazole group. A listing of these subjects will be provided.

Numbers and proportions of subjects with postdose values of fasting low-density lipoprotein (LDL) cholesterol, high-density lipoprotein (HDL) cholesterol, triglyceride, and blood glucose meeting the criteria for changes in glucose and lipid metabolism-related parameters (Table 9.3-1) will be determined by baseline value for each treatment group and for the overall brexpiprazole group. A listing of these subjects will be provided.

Table 9.3-1 Changes in Glucose and Lipid Metabolism-related Parameters		
LAB PARAMETER	BASELINE	ANYTIME POST BASELINE
LDL Cholesterol, Fasting (mg/dL)	Borderline 100-<160 Normal/Borderline <160 Normal <100 Any Value	High >=160 High >=160 Borderline/High >=100 Increased >=30
HDL Cholesterol, Fasting (mg/dL)	Normal >=40 Any Value	Low <40 Decreased >=20
Triglycerides, Fasting (mg/dL)	Normal <150 Borderline 150-<200 Normal/Borderline <200 Normal <150 Normal/Borderline/high <500 Any Value	High 200-<500 High 200-<500 High 200-<500 Borderline/High/Very High >=150 Very High >=500 Increased >=50
Glucose Fasting, Serum (mg/dL)	Normal <100 Impaired 100-<126 Normal/Impaired <126 Any Value	High >=126 High >=126 High >=126 Increased >=10

Numbers and proportions of subjects not meeting the metabolic syndrome criteria (Table 9.3-2) at baseline and meeting the criteria after treatment will be determined for each treatment group and for the overall brexpiprazole group. A listing of these subjects will be provided.

Table 9.3-2 Metabolic Syndrome Criteria	
Description	Metabolic Syndrome Criteria (Health, Labour and Welfare Ministry of Japan)
Central obesity	Waist Circumference ≥ 85 cm (Male), ≥ 90 cm (Female)
Dyslipidemia	Triglycerides, Fasting ≥ 150 mg/dL and/or HDL, Fasting <40 mg/dL
Supine blood pressure	Systolic ≥ 130 mmHg and/or Diastolic ≥ 85 mmHg
Glucose fasting, serum	≥ 110 mg/dL
Metabolic syndrome	met central obesity criteria and 2 of 3 other criteria at a visit

For each quantitative laboratory parameter in the antidepressant treatment period (Phase A), descriptive statistics of actual measurements and changes from baseline (before the

start of the antidepressant treatment period [Phase A]) at each time point and the last assessment time point will be calculated overall and for each requisite concomitant medication in the ADT set. A listing of subjects with laboratory test values meeting the criteria for potentially clinically significant laboratory test values (Appendix 2) will be provided.

For each quantitative laboratory parameter in the antidepressant treatment period (Phase A) and the antidepressant-responder treatment-continuation period (Phase A+), descriptive statistics of actual measurements and changes from baseline (before the start of the antidepressant treatment period [Phase A]) at each time point and the last assessment time point will be calculated overall and for each requisite concomitant medication in the Phase A+ set. A listing of subjects with laboratory test values meeting the criteria for potentially clinically significant laboratory test values (Appendix 2) will be provided.

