7.6 Safety Analysis

Safety analysis for the double-blind period (Phase B) will be performed using the safety analysis set. Baseline is defined as Week 8 of the antidepressant treatment period (Phase A).

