7.6.2 Clinical Laboratory Data

For each quantitative laboratory parameter, descriptive statistics of actual measurements and changes from baseline at each time point will be calculated for each treatment group and for the overall brexpiprazole group.

For each laboratory parameter (excluding qualitative parameters), actual measurements will be classified as "lower than the lower limit of the reference range," "within the reference range," and "higher than the upper limit of the reference range" using the reference range specified by the central laboratory, and a shift table from baseline will be produced for each treatment group and for the overall brexpiprazole group.

For each qualitative laboratory parameter, a shift table from baseline will be produced for each treatment group and for the overall brexpiprazole group.

Numbers and proportions of subjects with potentially clinically significant laboratory test values will be determined for each treatment group and for the overall brexpiprazole group.

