The mean plasma brexpiprazole concentration over time and individual values at each time point after the most recent dosing will be plotted by treatment group. Plotted diagrams by CYP2D6 phenotype in each treatment group and by requisite concomitant medication in each treatment group will also be provided in the same manner.

Scatter plots of plasma brexpiprazole concentrations over time will be provided by treatment group. Scatter plots by CYP2D6 phenotype in each treatment group and by requisite concomitant medication in each treatment group will also be provided in the same manner.

Plasma brexpiprazole concentrations below the lower limit of quantitation will be handled as 0 (ng/mL) when their descriptive statistics are calculated and when plotted diagrams and scatter plots are created.

11 Pharmacodynamic Analyses

Not applicable.

12 Pharmacogenomic Analyses

CYP2D6 genotype (phenotype) will be tabulated as specified in [Section 7.2 Demographic and Baseline Characteristics](#). CYP2D6 phenotype will also be summarized in subgroup efficacy and safety analyses.

13 Interim Analysis

No interim analyses are planned.

14 Changes in the Planned Analyses

- The following changes were made to categorical analyses of QTc:
Only subjects with postdose QTc meeting the criteria will be summarized, instead of summarization at all time points.

Only subjects with QTc not meeting the criteria at baseline and meeting the criteria after baseline will be summarized.
- It has been decided that CYP2D6 phenotype will be tabulated as specified in [Section 7.2 Demographic and Baseline Characteristics](#). CYP2D6 phenotype will also be summarized in subgroup efficacy and safety analyses.
- The original plan of using the LOCF dataset in ANCOVA of safety endpoints was changed as follows: Measurements at each time point and at the last assessment time point and, as necessary, the worst postdose measurement will be included in the analysis.
- The original plan of calculating descriptive statistics of plasma brexpiprazole concentrations by treatment group in pharmacokinetic analysis was changed as follows: Descriptive statistics of plasma brexpiprazole concentrations at each time point after the most recent dosing, trough concentrations, and plasma drug concentrations at all time points will be calculated by treatment group, by CYP2D6 phenotype in each treatment group, and by requisite concomitant medication in each treatment group.

15 References

Not applicable.

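### The Phase B table and listing of clinically significant laboratory values omit subjects who already met the criterion at Week 8, a narrowing of the protocol that SAP section 14 does not declare

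*SAP*

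**What the plan says.** Protocol 7.6.2 states the analysis in one sentence with no baseline condition: "Numbers and proportions of subjects with potentially clinically significant laboratory test values will be determined for each treatment group", and likewise for the pooled brexpiprazole group. Protocol 7.6 sets baseline for Phase B safety at Week 8 of Phase A.

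SAP 9.3 narrows this to "laboratory test values not meeting the criteria for potentially clinically significant laboratory test values (Appendix 2) at baseline and meeting the criteria after treatment". It then adds "A listing of these subjects will be provided", so the listing carries the same restriction as the count. In Appendix 5 these outputs are CT-10.3.1 (incidence) and CT-10.3.2 (listing). Neither title mentions the restriction.

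For Phase A, and in the same terms for Phase A+, SAP 9.3 sets no baseline condition: "A listing of subjects with laboratory test values meeting the criteria for potentially clinically significant laboratory test values (Appendix 2) will be provided".

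SAP section 14, which records departures from the protocol's planned analyses, declares the equivalent change for QTc: "Only subjects with QTc not meeting the criteria at baseline and meeting the criteria after baseline will be summarized". It has no such entry for laboratory values.

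**The concern.** A treatment-emergent count is a reasonable summary. The difficulty is that here it replaces the broader count and also governs the listing. A subject who enters Phase B already meeting a criterion can worsen to any extent without appearing in the one table and the one listing designed to show individual laboratory values of clinical relevance. These are subjects in whom further deterioration would matter to a safety reader. From the title of CT-10.3.2, that reader would take the listing to be complete.

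The SAP treats other safety data differently. Under Appendix 1 (vital signs) and the heart rate, PR and QRS rows of Appendix 3 (ECG), a value must pass the limit and also differ from baseline by a stated amount. A subject who starts beyond the limit and worsens by that amount is kept.

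**Working it through.** The plan states no figure to reproduce. The check has three steps: whether a subject can meet a criterion at Week 8, what the rule then does, and which other outputs would show the worsening.

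**1. Can a subject meet Appendix 2 at Week 8?**

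The numeric laboratory exclusions (Protocol Table 3.4.3-1) apply at screening, Day -28 to -1. The Week 8 visit is nominally Day 57. The gap is 56 + 1 = 57 days to 56 + 28 = 84 days, or about 8 to 12 weeks. The criteria for proceeding to Phase B (inclusion criteria 9 to 12) contain no laboratory test. Comparing screening exclusions with Appendix 2:

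| Test | Excluded at screening | Flagged by Appendix 2 |
|---|---|---|
| Haemoglobin | ≤ 9 g/dL | ≤ 11.5 (men), ≤ 9.5 (women) |
| CPK | > 3 × ULN | ≥ 3 × ULN |
| AST, ALT | > 2 × ULN | ≥ 3 × ULN |
| Creatinine | ≥ 2 mg/dL | ≥ 2.0 mg/dL |
| Platelets | ≤ 75,000/mm³ | ≤ 75,000/mm³ (low limit) |
| Absolute neutrophils | ≤ 1000/mm³ | ≤ 1,000/mm³ |
| ALP, LDH, BUN, uric acid, bilirubin, total cholesterol, electrolytes | no numeric limit | limit given |

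A man with haemoglobin 10.5 g/dL is eligible and already flagged. For AST, ALT, creatinine, platelets and neutrophils, and essentially for CPK, the abnormality would have to arise after screening. Nothing in the Phase B entry criteria prevents that.

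**2. What the rule does**

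The rule is: counted = (criterion not met at Week 8) and (criterion met after dosing). The values below are illustrative, not trial data.

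| Week 8 → post-dose | CT-10.3.1 and CT-10.3.2 | Other targeted count in SAP 9.3 |
|---|---|---|
| CPK 2.9 → 3.0 × ULN | in | not needed |
| CPK 3 → 30 × ULN | out | none |
| ALT 3 → 15 × ULN, bilirubin 1 × ULN | out | none |
| ALT 3 → 15 × ULN, bilirubin 2.5 × ULN | ALT out | Hy's Law |
| Haemoglobin, man, 10.5 → 7 g/dL | out | none |
| Total cholesterol 245 → 400 mg/dL | out | none |
| Prolactin 1.5 → 6 × ULN | out | tiers > 2 and > 3 × ULN |
| Prolactin 3.5 → 20 × ULN | out | none |
| Fasting triglycerides 160 → 480 mg/dL | out | rise 320 ≥ 50, Table 9.3-1 |
| Fasting glucose 105 → 180 mg/dL | out | rise 75 ≥ 10, Table 9.3-1 |
| Fasting LDL 165 → 260 mg/dL | out | rise 95 ≥ 30, Table 9.3-1 |

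**3. Where other routes exist**

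- The Hy's Law count has no baseline condition: "Numbers and proportions of subjects with postdose values of alanine aminotransferase (ALT), aspartate aminotransferase (AST), and total bilirubin (TBL) meeting Hy's Law criteria".
- Table 9.3-1 has rows open to any baseline value for fasting LDL, HDL, triglycerides and glucose.
- The prolactin tiers catch a subject who moves from a lower tier to a higher one.
- The haematocrit and urine protein and glucose criteria are themselves changes from baseline. They cannot be met at baseline, so they lose nobody.

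No other targeted route exists for CPK, isolated ALT or AST, ALP, LDH, BUN, creatinine, uric acid, isolated bilirubin, total cholesterol, electrolytes, haematology other than haematocrit, or prolactin already above 3 × ULN. The reference-range shift table shows such a subject only as high to high or low to low.

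**The case against.** A reader might infer that these subjects are neither counted nor listed anywhere. The documents do not support that.

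- **Adverse events.** Protocol 5.1 makes a laboratory value an adverse event if the investigator judges it medically relevant, if it leads to discontinuation, or if it meets the criteria for a serious event. Protocol 5.2 assesses Phase B events against the Week 8 condition and requires a worsened event to be reported anew. CPK elevation has its own table, CT-8.9.3.
- **Extremes.** SAP 7.2 defines descriptive statistics to include the minimum and maximum, and SAP 9.3 applies them to actual values and changes. A CPK of 30 × ULN could appear as an arm's maximum.
- **Full listings.** LAB-1.1 to LAB-4.1 give laboratory results for randomized subjects.

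These points stand, but capture is partial. The first route depends on investigator judgement. The second shows an extreme without the subject's course. The third is unfiltered, for a planned 720 subjects.

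It is also fair to say that requiring a criterion to be newly met is a convention the SAP uses elsewhere (prolactin tiers, metabolic syndrome, QTc). The Phase A and A+ outputs are non-comparative listings, not a rival version of the same count. The rule applies equally to placebo, so it is not aimed at active drug. Finally, protocol 7.6.2 is a single general sentence, and protocol section 7 leaves detailed methods to the SAP. This softens the conflict with the protocol. It does not explain why section 14 records the change for QTc and omits it here, or why the listing as well as the count had to be narrowed.

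**Conclusion.** The point holds for CT-10.3.1 and CT-10.3.2. Followed as written, SAP 9.3 leaves marked Phase B worsening from an already flagged Week 8 value out of both outputs. For the tests without another route, no other targeted laboratory output replaces them. The restriction is absent from protocol 7.6.2 and undeclared in SAP section 14.

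The number of subjects affected cannot be derived, because the documents give no Week 8 laboratory rates. A reader might reason that a prevalence of 1% to 2% would remove 0.01 × 240 = 2.4 to 0.02 × 240 = 4.8 subjects per arm. That prevalence would be pure assumption, and it counts everyone flagged at Week 8, not those who then worsen.

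Nor do the documents show that the reported proportions would be materially understated. The SAP does not state the denominator. With, say, 4 new cases and 5 subjects already flagged, 4/240 = 1.67% against 4/235 = 1.70%.

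This is a gap in descriptive safety reporting. It does not bear on the primary or any other efficacy analysis. The conclusion rests only on the wording of the rule and on the eligibility limits.

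**What to change.** 1. In SAP 9.3, make CT-10.3.2 list every Phase B subject with a post-dose value meeting Appendix 2. Show the baseline value and whether the criterion was already met at baseline.
2. In CT-10.3.1, keep the treatment-emergent row and add protocol 7.6.2's count of all subjects meeting Appendix 2 after dosing. Do not add a condition that the value be more abnormal than at baseline. The protocol has none, and it would admit trivial movements such as 3.2 to 3.3 × ULN while appearing to select real worsening.
3. Record the treatment-emergent restriction in SAP section 14, as is done for QTc.

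No new data, visits or clinical rules are needed. The cost is a few lines of SAP text, one added row and a longer listing. The downside is somewhat higher counts in all arms, including some chronic abnormalities, which the baseline column lets the reader recognise.
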